6.1.7 Route of Administration – Oral

6.1.8 Toxicity - The incidence of adverse events in the 158 patients in the Anaplastic Astrocytoma study for whom data are available. In the absence of a control group, it is not clear in many cases whether these events should be attributed to temozolomide or the patients' underlying conditions, but nausea, vomiting, fatigue and hematologic effects appear to be clearly drug-related. The most frequently occurring side effects were nausea, vomiting, headache and fatigue. The adverse events were usually NCI Common Toxicity Criteria (CTC) Grade 1 or 2 (mild to moderate in severity) and were self-limiting, with nausea and vomiting readily controlled with antiemetics. The incidence of severe nausea and vomiting (CTC grade 3 or 4) was 10% and 6%, respectively. Myelosuppression (thrombocytopenia and neutropenia) was the dose-limiting adverse event. It usually occurred within the first few cycles of therapy and was not cumulative.

Myelosuppression occurred late in the treatment cycle and returned to normal, on average, within 14 days of nadir counts. The median nadirs occurred at 26 days for platelets [range 21-40 days] and 28 days for neutrophils [range 1-44 days]. Only 14% (22/158) of patients had a neutrophil nadir and 20% (32/158) of patients had a platelet nadir which may have delayed the start of the next cycle. (See **WARNINGS**). Less than 10% of patients required hospitalization, blood transfusion or discontinuation of therapy due to myelosuppression.

In clinical trial experience with 110-111 women and 169-174 men (depending on measurements), there were higher rates of Grade 4 neutropenia (ANC < 500 cells/ μ L) thrombocytopenia (< 20,000 cells/ μ L) in women than men in the first cycle of therapy: (12% versus 5% and 9% versus 3%, respectively).

In the entire Safety database for which hematologic data exist (N= 932), 7% (4/61) and 9.5% (6/63) of patients over age 70 experienced Grade 4 neutropenia or thrombocytopenia in the first cycle, respectively. For patients less than or equal to age 70, 7% (62/871) and 5.5% (48/879) experienced Grade 4 neutropenia or thrombocytopenia in the first cycle, respectively.

Data released by the European Organization for Research and Treatment of Cancer (EORTC) in January 2014 shows that amongst 44 patients receiving temozolomide

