8. STUDY CALENDAR

Baseline evaluations are to be conducted within 2 weeks prior to start of protocol therapy. Scans and x-rays must be done \leq 4 weeks prior to the start of therapy. In the event that the patient's condition is deteriorating, laboratory evaluations should be repeated within 48 hours prior to initiation of the next cycle of therapy.

	Pre-study	C1 Wk 1	C1 Wk 2	C1 Wk 3	C1 Wk 4	Cx Wk 1 ^f	Cx Wk 2	Cw Wk 3	Cx Wk 4	Off study
Physical exam	X	X				X				X
Neurologic exam	X ^d									
MMSE	X ⁱ									
Vital signs	X	X								X
Heights	X									
Weight	X	X								X
Performance Status	X	X								X
CBC w/diff, plts	X	X	X	X	X	X ^j			X ^j	X
Serum chemistry^a	X	X	X	X	X	X				X
Serum tumor specific tumor markers^g	X									X
EKG (as indicated)	X	X								
Adverse event evaluation			X	X	X	X	X			
Tumor measurements^h	X	Tumor measurements are repeated at week 8, then every 8 weeks. Documentation (radiologic) must be provided for patients removed from study for progressive disease.								X
B-HCG	X ^b									
Pharmacokinetics^e, Lab Correlates		X ^c								

- a: Albumin, alkaline phosphatase, total bilirubin, bicarbonate, BUN, calcium, chloride, creatinine, glucose, LDH, phosphorus, potassium, total protein, SGOT [AST], SGPT [ALT], sodium.
- b: Serum pregnancy test (women of childbearing potential).
- c: See section 7.0. Pharmacokinetics will be done during week 1.
- d: All patients will be evaluated by a staff Neurologist prior to initiation of treatment and then will undergo frequent (every 4-8 hours) neurologic checks by a CRU RN during the 1-day inpatient CRU stay on cycle 1, day1.
- e: Pharmacokinetics will be obtained for the first cycle only.
- f: Subsequent cycles and associated evaluations may be conducted within +/- 2 days of the previous cycle.
- g: Tumor specific tumor markers to be obtained per physician discretion (CEA, CA 19-9, CA 125, etc) if appropriate.
- h: For cohort A, CT of the chest, abdomen and pelvis will be obtained. For cohort B, CT of the chest, abdomen and pelvis as well as MRI of the brain will be obtained if malignancy is a non-CNS primary. For primary brain tumors, CT of the chest, abdomen and pelvis not required.
- i: MMSE to be done at screening for subjects in Cohort B only. These subjects must have a score of < 15. See appendix D.
- j: CBCs to be done Days 1 and 22 for Cycles 2 and beyond, for both Cohorts.

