9.1.3 Target Lesions

All measurable lesions up to a maximum of five lesions per organ and 10 lesions in total, representative of all involved organs, should be identified as **target lesions** and recorded and measured at baseline. Target lesions should be selected on the basis of their size (lesions with the longest diameter) and their suitability for accurate repeated measurements (either by imaging techniques or clinically). A sum of the longest diameter (LD) for all target lesions will be calculated and reported as the baseline sum LD. The baseline sum LD will be used as reference by which to characterize the objective tumor response.

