12. STATISTICAL CONSIDERATIONS

For cohort A, a maximum of 36 patients can theoretically participate on this study, based on 6 dose levels with a maximum of 6 patients at each dose level. However, given the fact that a 10-fold increase in MX is being tested in 6 consecutive dose escalation levels it is highly unlikely that the maximum number of patients will need to be enrolled at each level.

For cohort B, a maximum of 42 patients can theoretically participate on this study, based on 7 dose levels with a maximum of 6 patients at each dose level. However, given the fact that a 1.5-fold increase in TMZ and a 10-fold increase in MX is being tested in 7 dose escalation levels it is highly unlikely that the maximum number of patients will need to be enrolled at each level.

The following table gives the probabilities of escalating under given true but unknown underlying rates of DLT:

True Underlying DLT Rate	0.1	0.2	0.3	0.4	0.5
Escalate to next full dose	0.91	0.71	0.49	0.32	0.17
Do not escalate; prior dose level is MTD	0.09	0.29	0.51	0.68	0.83

Thus, if the true underlying rate of DLT is 20%, there will be a 71% chance of escalating to next full dose and a 29% chance that the lower dose will be chosen as the MTD.

The baseline levels (at 0h) of AP sites and DNA strand breaks will be compared to the levels at various time points (i.e. 2h, 4h and 122h) after treatment by paired T-test or Wilcoxon rank sum test. The predictive value of PK parameters (e.g. AUC, C_{max}), levels of AP sites and levels of DNA strand breaks on clinical response and grade 3/4 toxicity will be examined by logistic regression after adjusting the dose level; their predictive value on time to event outcomes, such as disease progression free survival, will be tested using (extended) Cox model after controlling other factors including dose level.

REFERENCES

1. L Liu, P Taverna, CM Whitacre, S Chatterjee, and SL Gerson. Pharmacologic disruption of base excision repair sensitizes mismatch repair-deficient and -proficient colon cancer cells to methylating agents. *Clin Cancer Res* 5:2908-2917, 1999.
2. L Liu, Y Nakatsuru, and SL Gerson. Base excision repair as a therapeutic target in colon cancer. *Clin Cancer Res* 8:2985-2991, 2002.
3. L Liu, JR Donze, and SL Gerson. Methoxyamine enhances antitumor efficacy of BCNU in colon tumor xenografts. *Proc Amer Assoc Cancer Res* 43:794 (#3938), 2002.

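### Toxicity and tumour response are related to PK and DNA-damage markers only through yes/no outcomes; full-scale outcomes from data already collected would add useful power for markers not closely tied to dose

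*Combined protocol and SAP*

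**What the plan says.** Section 12 names as predictors the PK parameters (AUC and Cmax are the examples), AP-site levels and strand-break levels. Their value "on clinical response and grade 3/4 toxicity will be examined by logistic regression after adjusting the dose level". The toxicity cut is explicit. That response is yes/no follows from the method and is not spelled out.

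The same sentence continues: "their predictive value on time to event outcomes, such as disease progression free survival, will be tested using (extended) Cox model", controlling for dose level among other factors.

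Finer data are already collected:

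- **Blood counts.** The Section 8 calendar marks a CBC before study and in each week of cycle 1. Its footnote adds "CBCs to be done Days 1 and 22 for Cycles 2 and beyond, for both Cohorts". Section 11 has a weekly lab form.
- **Toxicity grades.** Section 10 grades adverse events under CTCAE v3.0.
- **Lesion sums.** Section 9.1.3 records the sum of longest diameters: "The baseline sum LD will be used as reference by which to characterize the objective tumor response".

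Section 12 plans no analysis of count nadirs, ordered grade or percentage lesion change. For the predictive models it gives no alpha, effect size, event rate or power, and it does not say whether toxicity is counted in cycle 1 or in all cycles.

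**The concern.** The predictors are continuous, while both logistic outcomes are cuts of finer measurements. In a sample this small, a cut that few patients cross leaves few events to model.

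Marrow toxicity is where this is most likely to matter. Section 6.1.8 says of temozolomide: "Myelosuppression (thrombocytopenia and neutropenia) was the dose-limiting adverse event". Section 6.2.3 reports that temozolomide neutropenia in rats deepened as the methoxyamine dose rose. That is a graded effect, and a grade 3/4 indicator can miss it. The abstract in Appendix B describes five patients on the earlier five-day infusion: anaemia, leukopenia and lymphopenia occurred at grades 1-2, with no treatment-related event of grade 3 or higher. All five would score zero on a treatment-related grade 3/4 outcome.

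At stake is a null result on the cut being read as evidence that exposure or DNA damage is unrelated to marrow toxicity.

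**Working it through.** **Sample size.** Section 12 gives no N for these models, only accrual ceilings. For cohort A: "a maximum of 36 patients can theoretically participate on this study, based on 6 dose levels", 6 × 6 = 36. For cohort B: "a maximum of 42 patients can theoretically participate on this study, based on 7 dose levels", 7 × 6 = 42. Both reproduce. The plan adds that "it is highly unlikely that the maximum number of patients will need to be enrolled at each level", so I use N = 36 as the base case. (The cohort A table in Section 4.1 lists seven positive levels, and level 1 is expanded to 10, which gives 10 + 6 × 6 = 46. Those sections need reconciling; the conclusion here does not depend on it.)

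**Event rates.** The nearest figures are in Section 6.1.8, for temozolomide alone: first-cycle grade 4 neutropenia 12% in women and 5% in men, grade 4 thrombocytopenia 9% and 3%, and grade 3/4 nausea and vomiting 10% and 6%. None is the rate of the planned endpoint, so I take 5-50% as a range.

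**Step 1: information lost by the cut.** For a normal underlying outcome cut so that a fraction p are events, the information kept is φ(z_p)² / [p(1 − p)]. At p = 0.10, φ = 0.1755, so 0.0308 / 0.09 = 0.34 is kept and 66% is lost.

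| Event rate | 5% | 10% | 15% | 20% | 25% | 30% | 50% |
|---|---|---|---|---|---|---|---|
| Lost | 78% | 66% | 57% | 51% | 46% | 42% | 36% |

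More than half is lost only below about 21% (or above about 79%). At 5% and N = 36, the chance of no event at all is 0.95^36 = 0.16, and the model then cannot be fitted.

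**Step 2: effect of the planned dose adjustment.** Assume an exposure-outcome correlation of 0.4 and a marker-dose correlation ρ. The dose-adjusted partial correlation is 0.4√(1 − ρ²) / √[0.16(1 − ρ²) + 0.84].

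- ρ = 0: 0.40
- ρ = 0.5: 0.346 / 0.980 = 0.354
- ρ = 0.94: 0.136 / 0.927 = 0.147

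Approximate power of a linear model, two-sided 5%, is Φ(atanh(r)·√(36 − 4) − 1.96). This gives 67%, 55% and 13%.

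**Step 3: simulated power with dose in the model** (N = 36, correlation 0.4, likelihood-ratio test for the logistic model, 10-30% events).

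| Marker-dose correlation | Continuous | Ranked grade | Logistic |
|---|---|---|---|
| 0 to 0.5 | 58-66% | 52-61% | 28-49% |
| 0.5 alone | 58% | 52% | 28-40% |
| about 0.94 | 13% | - | 10% |

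The simulation agrees with Step 2 to within about 3 points. At ρ = 0.5 the continuous outcome gains 58 − 40 = 18 to 58 − 28 = 30 points; at ρ = 0.94 it gains about 3.

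**Step 4: sensitivity.** With the dose-adjusted partial correlation itself fixed at 0.4:

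| N | Continuous | Logistic, 10% events | 20% | 30% |
|---|---|---|---|---|
| 36 | 66-70% | 12 / 31% | 27 / 41% | 36 / 47% |
| 42 | 75-79% | 18 / 37% | 38 / 48% | 47 / 53% |
| 78 (both cohorts) | 94-97% | 51 / 58% | 66 / 70% | 78 / 81% |

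Logistic entries are Wald / likelihood ratio. The likelihood-ratio figures are somewhat optimistic when events are few: at N = 20 the false-positive rate reached 7-13%.

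**Step 5: the Cox model.** Power is Φ(√[events × (1 − 0.5²)]·ln HR − 1.96). With 36 events and HR 1.5 per SD: 5.196 × 0.405 − 1.96 = 0.147, or 56%. With HR 1.8 it is 86%. The efficacy side therefore keeps much of its information if most patients progress.

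**The case against.** **The efficacy side has another analysis.** A reader might infer that the logistic models are the only link from the markers to tumour effect. They are not: the Cox model follows in the same sentence. This point stands for efficacy. It does nothing for toxicity, and progression-free survival does not directly test objective 1.4, which treats strand breaks as a surrogate for tumour response.

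**Methoxyamine exposure may simply follow dose.** Section 4.1 escalates methoxyamine tenfold, from 15 to 150 mg/m². With an assumed 25-35% between-patient variability, exposure and log dose correlate at 0.92-0.96. Under those assumptions, at 30-40 patients and correlations of 0.4-0.5, power was 11-25% for the linear model and 10-17% for the logistic, a gain of about 0 to 12 points. This also stands: once dose is in the model, neither analysis is useful for such a marker. The gain belongs to predictors less tied to dose, which may include strand breaks and temozolomide PK.

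**The cut may not be rare.** The marrow rates in Section 6.1.8 are grade 4 only, one event type at a time, first cycle, temozolomide alone. Any grade 3/4 event on the combination could be commoner, and no response rate is given. So the documents do not establish that most of the information is lost.

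**Counts do not cover the main safety concern.** The two DLTs described in Section 4.1 are psychosis and allergic reaction, and the special monitoring in Section 4.2 is neurologic. That is why an ordered-grade analysis is needed beside the counts.

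**These models are secondary.** None of the four objectives is predictive, and no power is claimed. This argues for adding exploratory analyses and against replacing the planned ones. It is no reason to leave recorded data unused.

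**Conclusion.** The point holds in a limited form. For toxicity and response, Section 12 plans only dose-adjusted logistic regression on cut outcomes, and toxicity has no other analysis of the markers. The information lost is about 50-80% if events occur in 5-20% of patients and about 36-42% at 30-50%. For a marker correlated with dose at 0.5 or less, a full-scale outcome raises power from 28-49% to about 58-66% (52-61% for ranked grade). For exposure that closely tracks dose, the gain is about 3 points.

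These figures rest on assumptions the plan does not supply: N = 36, an exposure-outcome correlation of 0.4, a normal underlying outcome and the stated event rates. A reader might go further and conclude that most of the power is lost whatever the event rate, or that the change would rescue the methoxyamine AUC and Cmax analyses. The calculations support neither.

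**What to change.** In Section 12, keep the logistic and Cox models, define the toxicity window, and add these as exploratory analyses with the same dose-level adjustment:

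1. **Haematologic toxicity.** Linear regression of log(nadir/baseline) for ANC and platelets, using the weekly cycle 1 counts plus the cycle 2 day 1 count. State an analysis rule for platelet counts after transfusion, since Section 4.3 permits blood products. Growth factors are not given in cycle 1, so they will not distort these nadirs.
2. **Non-haematologic toxicity.** Proportional-odds regression of worst cycle 1 CTCAE grade, including neurologic events.
3. **Tumour effect.** Percentage change in the sum of longest diameters for patients with measurable disease and a follow-up scan, or ordered best response (PD/SD/PR/CR), which keeps early progressors in the analysis.

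The cost is plan wording and some analysis time, with no new visits, samples or patients. There are three downsides. Weekly counts may miss or truncate the nadir: Section 6.1.8 gives medians of day 26 for platelets and day 28 for neutrophils, with ranges to days 40 and 44. Lesion change will be missing for some patients. There will also be a few more exploratory tests, which should be reported as such.

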APPENDIX A

Performance Status Criteria

ECOG Performance Status Scale		Karnofsky Performance Scale	
Grade	Descriptions	Percent	Description
0	Normal activity. Fully active, able to carry on all pre-disease performance without restriction.	100	Normal, no complaints, no evidence of disease.
		90	Able to carry on normal activity; minor signs or symptoms of disease.
1	Symptoms, but ambulatory. Restricted in physically strenuous activity, but ambulatory and able to carry out work of a light or sedentary nature (e.g., light housework, office work).	80	Normal activity with effort; some signs or symptoms of disease.
		70	Cares for self, unable to carry on normal activity or to do active work.
2	In bed <50% of the time. Ambulatory and capable of all self-care, but unable to carry out any work activities. Up and about more than 50% of waking hours.	60	Requires occasional assistance, but is able to care for most of his/her needs.
		50	Requires considerable assistance and frequent medical care.
3	In bed >50% of the time. Capable of only limited self-care, confined to bed or chair more than 50% of waking hours.	40	Disabled, requires special care and assistance.
		30	Severely disabled, hospitalization indicated. Death not imminent.
4	100% bedridden. Completely disabled. Cannot carry on any self-care. Totally confined to bed or chair.	20	Very sick, hospitalization indicated. Death not imminent.
		10	Moribund, fatal processes progressing rapidly.
5	Dead.	0	Dead.

APPENDIX B

Submitted Abstract:

Unexpected prolonged half life of the base-excision repair inhibitor Methoxyamine (MX) given with Temozolomide (TMZ) in the first in human phase 1 clinical trial

Author Block: *[name], [name], [name], [name].* Ireland Cancer Ctr., Cleveland, OH, Ireland Cancer Center, Cleveland, OH

Abstract:

Background: MX is the first base excision repair (BER) inhibitor evaluated in humans. MX blocks the BER pathway by covalently binding to apurinic/pymidinic (AP) sites in DNA. In several preclinical studies, improved therapeutic efficacy has been demonstrated with various chemotherapeutic agents including alkylating agents, such as TMZ. Initial results and correlative studies of the first in humans administration of MX are presented.

Methods: This ongoing phase I dose-escalation trial investigates the safety, pharmacokinetic (PK) and pharmacodynamic (PD) profile of MX given as an intravenous continuous infusion (CI) for 5 days in combination with TMZ given orally for 5 days on a 28-day cycle. PD markers, including analysis of AP sites measured on DNA extracted from patients' mononuclear cells (PBMCs) as well as DNA strand break determined by comet assay at multiple time points during the 5-day treatment with MX and TMZ, are included.

Results: 5 patients with metastatic solid tumors have enrolled, 4 at dose-level (DL) 1 (TMZ 100 mg/m²/day, x5days and MX 15 mg/m²/day, x5days CI) and 1 at DL 2 (TMZ 150 mg/m²/day, x5days, MX at same dose as in DL 1). Primary tumors include colon cancer (n=2), head and neck cancer (n=1), radiation-associated sarcoma (n=1), thymic carcinoma (n=1). Treatment has been well tolerated. No treatment-related AEs leading to dose reduction, interruption or discontinuation were reported. No grade 3 or higher treatment related toxicities or AEs have occurred. Grades 1-2 toxicities observed include: nausea, vomiting, fatigue, fever, dyspnea on exertion, anemia, leukopenia, lymphopenia, hypophosphatemia, dyspnea on exertion, nystagmus.

PK analyses on samples from the 5 patients included in the study revealed a distinct PK profile different from the one observed in rats and dogs, where half-life of MX was estimated to be 19 minutes and 4.5 hours respectively. In humans, MX half life is estimated to be 45.3 hours (range: 32 - 68.8 hours).

An increase in formation of AP sites over time in cells was detected after patients received a single dose of TMZ (100 mg/m²), reaching the highest levels 2 or 4 h after TMZ in different patients.

Administration of the combination of TMZ and MX resulted in at least 60% reduction in detectable AP sites, due to the binding of MX to AP sites to form MX-bound AP sites.

Comet assay in PBMCs following treatment with the combination of MX and TMZ detected a 1.5 to 3-fold increase of DNA strand breaks compared to single dose of TMZ.

Conclusions: Initial data from the first in humans MX phase I clinical trial demonstrate that MX in combination with TMZ is well tolerated. MX has a distinct PK profile in humans, corresponding to a 10-fold increase in estimated half-life when compared to the half-life observed in dogs. PD demonstration of MX's biologic activity on patients' mononuclear cells has been demonstrated even at the first dose level.

APPENDIX C

Simulation of One-Hour Infusion for a Cmax of 41.40 µg/L

User Defined Settings

PK Model 2 - [Untitled6]

Simulating data

1 compartment IV-Infusion, no lag time, 1st order elimination

$$C(T) = (D/TI) / V / K10 * (\exp(-K10 * TSTAR) - \exp(-K10 * T))$$

Parameter	Units	Estimate	VIF	Sqrt[VIF] P %
V	L	1437.27	0.13	0.81
K10	1/hr	0.015315	0.000000	2.75

[figure not shown]
Worksheet: Non-Transposed Final Parameters
(20-Jan-2009)

Constant	Value (mg)
Number of Doses	1
Dose #1	59.961
Start Time of Dose #1	0
End Time of Dose #1	1
Worksheet: Dosing (20-Jan-2009)	

Time_obs (hr)	Time (hr)	Predicted (ug/L)	VIF
0	0.0000	0.0000	0.0000
0.1	0.1000	4.1687	0.0011
0.2	0.2000	8.3310	0.0045
0.4	0.4000	16.6365	0.0179
0.6	0.6000	24.9166	0.0399
0.8	0.8000	33.1713	0.0703
1	1.0000	41.4008	0.1091
1.2	1.2000	41.2742	0.1074
1.4	1.4000	41.1480	0.1057
1.6	1.6000	41.0222	0.1041
1.8	1.8000	40.8967	0.1026
2	2.0000	40.7716	0.1011
5	5.0000	38.9408	0.0826
10	10.0000	36.0702	0.0663
15	15.0000	33.4113	0.0630
20	20.0000	30.9484	0.0677
24	24.0000	29.1094	0.0750
36	36.0000	24.2225	0.1032
45.26	45.2600	21.0199	0.1229

60	60.0000	16.7723	0.1417
72	72.0000	13.9566	0.1449
96	96.0000	9.6639	0.1287
[contact]	6.6915	0.0992
[contact]	4.6334	0.0699
[contact]	3.2083	0.0463
[contact]	1.9653	0.0250

Parameter	Units	Estimate	VIF	Sqrt[VIF] P %
AUC	hr*ug/L	2724.07573	4547.78338	2.48
K10_HL	hr	45.259956	1.546513	2.75
Cmax	ug/L	41.400843	0.109058	0.80
CL	L/hr	22.011503	0.000298	2.48
AUMC	hr*hr*ug/L	179234.144	85014379.981	5.14
MRT	hr	65.296315	3.218864	2.75
Vss	L	1437.270000	0.134888	0.81

X vs. Predicted Y
(20-Jan-2009)

